3.2.3 Two-week visit (contact lens group only)

Subjects should attend wearing their Biofinity lenses which should have been in situ for at least 2 hours. Subjects who attend without lenses in situ for at least 2 hours will usually be rescheduled. The following procedures will be performed (any ocular measurement procedures outlined below will be carried out on each eye):

1. Any medical or ocular issues since the last visit will be recorded.

2. [Redacted]

3. [Redacted]

4. [Redacted]

5. The CVS-Q questionnaire will be completed.

6. [Redacted]

7. [Redacted]

■ [Redacted]

■ [Redacted]

■ [Redacted]

■ [Redacted]

■ [Redacted]

■ [Redacted]

■ [Redacted]

■ [Redacted]

■ [Redacted]

■ [Redacted]

■ [Redacted]

■ [Redacted]

8. [Redacted]

9. [Redacted]

- [REDACTED]
- [REDACTED]
- [REDACTED]
- [REDACTED]
10. [REDACTED]
- [REDACTED]
11. The study lenses will be removed and stored in PureMoist disinfecting solution.
12. A complete biomicroscopic examination will be conducted as outlined in Section 3.2.2 following which the lenses will can be re-applied (after rinsing with saline) or given back to the subject to take home.
13. The subject will be discharged and asked to return for the one month visit wearing the study lenses which need to have been worn for at least 2 hours. Subjects should be asked to wear their lenses for a minimum of 8 hours per day, 5 days per week, and whilst using digital devices for at least 4 hours per day.

3.2.4 Visit 3: One month visit

For the contact lens group, subjects should attend wearing their Biofinity lenses which should have been in situ for at least 2 hours. Subjects who attend without lenses in situ for at least 2 hours will usually be rescheduled.

For the spectacle group, subjects should attend wearing (or having brought with them) the spectacles that they have been wearing for digital device use. Spectacles should have been worn for a minimum of 2 hours on the day of the visit.

For the contact lens group, this visit will be identical to the two week visit except that the contact lenses will be discarded at the end of the visit and they will be provided with a new pair of lenses.

For the spectacle group, the following will take place:

1. Any medical or ocular issues since the last visit will be recorded.
2. Spectacle wearing times since the previous visit will be recorded (hours per day, days per week and comfortable hours per day).
3. [REDACTED]
4. [REDACTED]
5. The CVS-Q questionnaire will be completed.
6. [REDACTED]

7. [REDACTED]
8. The subject will be discharged and asked to return for the two month visit wearing their spectacles. Subjects should be asked to wear their spectacles for a minimum of eight hours per day, five days per week, and whilst using digital devices for at least four hours per day.

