1.3 Study objectives

The aim of this clinical work is to compare the clinical performance and subjective acceptance of Biofinity Energys (CooperVision Inc.) contact lens when compared to single-vision spectacles in subjects who use digital devices (phones, tablets, laptops, desktop computers) for at least 4 hours per day on at least 5 days per week. Seventy-six subjects will be randomised to use either their habitual spectacles or the study contact lenses for two months. Subjects will be asked to complete the Computer Vision Syndrome Questionnaire (CVS-Q) at each visit which is a validated 16-item questionnaire designed to measure visual symptoms related to the use of digital devices. The CVS-Q investigates both 'internal' (burning, itching, tearing, redness, dryness) and 'external' symptoms (e.g. eye pain, double vision, headache, blurred vision).

[REDACTED]

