2.6.1.1 Use of lenses

Study contact lenses will be worn on a daily wear, re-useable basis. [REDACTED]

[REDACTED] The lenses will be disinfected and stored using PureMoist (Alcon Vision Care) and the use of comfort drops will not be allowed. The lenses are also to be worn for a minimum of 2 hours before attending the follow-up visits (CL group only).

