3.2.5 Two month visit

This study visit will be identical to the one month visit.

Additionally the following will be carried out:

1. At the final visit (or when the subject is discontinued at an earlier visit) the subject will sign a study exit statement acknowledging that the work is complete, although they may have been asked by the investigator to attend a post-study follow-up visit, and that they should continue to use their lenses (and solutions) as advised, and seek aftercare for their contact lenses. A copy of this signed form will be issued to the subject.
2. The subject will be issued with their payment and discharged.

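### Rebooking for under 2 hours of wear is stated for the lens arm only and moves the CVS-Q with the visit, so lens-arm scores from poor-tolerance days may be preferentially lost.

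*Combined protocol and SAP*

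**What the plan says.** Section 3.2.4 sets the attendance conditions for the one-month visit. Lens subjects should arrive with lenses in for at least 2 hours, and "Subjects who attend without lenses in situ for at least 2 hours will usually be rescheduled". Section 3.2.3 has the same rule for the two-week visit, which only lens subjects attend.

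For the spectacle arm, section 3.2.4 says that "subjects should attend wearing (or having brought with them) the spectacles" used for digital devices, and that "Spectacles should have been worn for a minimum of 2 hours on the day of the visit". It does not say what happens if this is not met. Section 2.6.1.1 also has a 2-hour rule before follow-up visits, limited to the lens group.

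Section 3.2.5 carries all of this to the two-month visit: "This study visit will be identical to the one month visit". These two visits are the only ones after randomisation that both arms attend.

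On the outcome, section 1.3 says: "Subjects will be asked to complete the Computer Vision Syndrome Questionnaire (CVS-Q) at each visit". In sections 3.2.3 and 3.2.4 the CVS-Q is step 5 of the visit, listed after the attendance condition. Section 1.4 describes the trial as open label, and section 1.5.1 bases the sample size on the CVS-Q.

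**The concern.** Both arms have the same 2-hour expectation, but only in the lens arm does missing it lead to a stated action, and that action moves the outcome measurement. The CVS-Q covers burning, itching, tearing, redness and dryness (section 1.3). These are plausible reasons for a first-time lens wearer to leave lenses out, particularly as comfort drops are not allowed (section 2.6.1.1). A lens subject who arrives without lenses for such a reason would usually be scored on another day, by which time the eyes may have settled. The timing of the score can then depend on the score itself, in one arm.

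The comparison is open label and rests on self-reported symptoms. Losing some poor-tolerance days from the lens arm would lower its mean CVS-Q and make lenses look better than they are. No visible text has the CVS-Q completed before rebooking, asks for the reason for non-wear, or says how a rebooked visit is analysed. Section 3.1.1 has data from unscheduled attendances recorded, but does not require a CVS-Q at them.

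**Working it through.** **1. The rules side by side (sections 3.2.4 and 3.2.5)**

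| | Lens arm | Spectacle arm |
|---|---|---|
| 2 hours of wear expected that day | Yes | Yes |
| May bring the correction rather than arrive wearing it | No | Yes |
| Stated consequence if under 2 hours | Usually rescheduled | None stated |
| CVS-Q at the visit | Step 5 | Step 5 |

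The difference lies in the stated consequence, not in the wear expectation.

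**2. The plan's own figure.** Inputs from section 1.5.1: SD 4.0, difference 3.2, power 90%. The significance level is not in the visible text. At two-sided 0.05, a two-sample t-test needs 33.8 per arm, rounded up to 34, which matches the plan; power at 34 per arm is 0.902. One-sided 0.05 would need 27 to 28 and does not match. Two-sided 0.05 is therefore assumed below.

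**3. Size of a possible shift.** Let p be the share of lens subjects rebooked, s the share of those rebookings due to symptoms, and d the amount by which the score on the skipped day would exceed the later recorded score. Rebookings for other reasons are taken to add nothing.

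Shift in the lens mean = p × s × d

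The documents give none of these values. The following are assumptions:

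- p = 10%, s = 50%, d = 2: 0.10 × 0.5 × 2 = 0.1 unit
- p = 10%, s = 100%, d = 2: 0.10 × 1 × 2 = 0.2 unit
- p = 20%, s = 50%, d = 4: 0.20 × 0.5 × 4 = 0.4 unit
- p = 20%, s = 100%, d = 4: 0.20 × 1 × 4 = 0.8 unit

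**4. Effect on error rates if there is no true difference.** The standard error of the difference is 4.0 × √(2/34) = 0.970, with 2 × 34 − 2 = 66 degrees of freedom. The noncentrality is shift / 0.970. The rejection rates come from the noncentral t distribution.

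| Shift (units) | Share of 3.2 | Noncentrality | Lenses wrongly declared better | Any two-sided rejection |
|---|---|---|---|---|
| 0 | 0% | 0 | 2.5% | 5.0% |
| 0.1 | 3.1% | 0.10 | 3.2% | 5.1% |
| 0.2 | 6.25% | 0.21 | 3.9% | 5.5% |
| 0.4 | 12.5% | 0.41 | 6.0% | 6.9% |
| 0.8 | 25% | 0.82 | 12.6% | 12.8% |

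The table shows what a given shift would do. It is not evidence that a shift of that size will occur.

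**The case against.** The case on the other side is substantial.

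- **The rule is not absolute and the bar is low.** Rescheduling is what usually happens, not what always happens. Two hours is little against the 8 hours per day asked of subjects, and someone with burning or dry eyes who has worn lenses for 2 hours is still scored. Lenses may also be out for unrelated reasons, such as an early appointment. A reader might infer that the lens arm is scored only on days when lenses are tolerable; the documents do not support that. However, the exceptions are left to an investigator in an open-label trial, which is not a safeguard.
- **The spectacle rule is silent, not lenient.** A reader might infer that a spectacle subject who merely brought the spectacles is always assessed. The text does not say so, and bringing them is compatible with having worn them earlier that day. What stands is that no consequence is stated.
- **Recall period.** The visible text gives none. If the CVS-Q looks back over more than the visit day, moving it within a 25 to 35 day window (Table 3) would not erase a bad spell, and the bias shrinks.
- **The score on the skipped day.** A subject without lenses is probably in spectacles or uncorrected. Nothing in the documents shows that the score would be higher that day; this is an assumption.
- **Other records.** Missed visits are followed up (section 3.1.2), ocular adverse events are recorded (section 2.3), and data are kept unless there are strong grounds for exclusion (section 2.1.1). Symptoms are not simply lost, but none of this secures a CVS-Q score on the day.
- **Redaction.** Steps 2 to 4 of the lens visits and most of the statistics section are blacked out. Related handling may be there.
- **Measuring with the assigned correction on** is a defensible aim. It justifies rebooking lens-on clinical measurements. It is a weaker reason to defer a questionnaire about symptoms.

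These points limit the size and certainty of the concern. They do not remove the one-sided rule.

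**Conclusion.** The point holds in a limited form. As written, the plan attaches rebooking for under 2 hours of wear to the lens arm alone, at both visits where the arms can be compared, and rebooking moves the CVS-Q. Where lenses are out because of symptoms that the CVS-Q would have picked up, the rule may preferentially remove poor-tolerance scores from the lens arm and favour lenses.

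The size is unknown. Under the assumed inputs above, false claims for lenses run from 3.2% to 12.6% against a nominal 2.5%, and the low end is close to negligible. The documents do not show that the lens arm's scores are confined to good days, or that the bias is large. Confidence is moderate. The change is still worth making, because the possible bias is directional, affects the score that sizes the trial, and is cheap to avoid.

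**What to change.** State in sections 3.2.4 and 3.2.5 that the CVS-Q is completed at the first attendance within each visit window, in both arms, before any rebooking and whatever correction is being worn, and that this score is used in the main comparison. Rebooking can stay for lens-on clinical measurements. If the CVS-Q is repeated at the rebooked visit, that score can serve as a sensitivity analysis. Record hours worn that day and the reason for any non-wear in both arms.

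Extending the rebooking rule to the spectacle arm would make the wording symmetric, but lens-arm scores would still be moved off days when lenses are out because of symptoms, so it would not remove the bias.

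The cost is about one protocol sentence and one or two eCRF fields, some of which may already exist in redacted steps. The sample size is unchanged. The downside is that a few lens-arm scores will be taken with lenses out.

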3.2.5 Two month visit

This study visit will be identical to the one month visit.

Additionally the following will be carried out:

1. At the final visit (or when the subject is discontinued at an earlier visit) the subject will sign a study exit statement acknowledging that the work is complete, although they may have been asked by the investigator to attend a post-study follow-up visit, and that they should continue to use their lenses (and solutions) as advised, and seek aftercare for their contact lenses. A copy of this signed form will be issued to the subject.
2. The subject will be issued with their payment and discharged.

3.2.6 Post-study follow-up visit

In the case of a subject who exits the study with significant clinical signs or symptoms, the investigator must undertake to examine the subject at intervals they determine to be clinically appropriate until the sign or symptom has resolved or returned to a level that is considered to be clinically acceptable. Details from these visits will be recorded on a post-study follow-up visit eCRF.

3.3 Monitoring subject compliance

Subjects are required to adhere to the instructions provided during this clinical investigation. This will be confirmed at the study visits by verbal questioning of the subject by the investigator.

3.4 Missing, unused and spurious data

The absence of any data will be carefully and critically considered. If appropriate, partial datasets will be included in the final analysis. Any data missing from a subject visit will be outlined in the report by indicating the number of subjects included for each analysis. Data that are unused or considered to be spurious will be detailed and discussed in the report.

Section 4. Study co-ordination

4.1 Document processing

All case report forms will be processed and evaluated by Eurolens Research, who will produce the final report with full statistical analysis. A draft report will be sent to the Industrial Contact Person in order to make comments and ask for re-drafts. If no comments are received from the Industrial Contact Person within eight weeks, a final report will be released with a separate document control page (in duplicate), requesting the Industrial Contact Person to sign both copies, one to keep and the other to be returned to Eurolens Research.

